4 STATISTICAL/ANALYTICAL ISSUES

4.1 Adjustments for covariates

The primary efficacy analysis will investigate the treatment effect, adjusting on the 2 randomization stratification variables:

- Region
 - North America, Western Europe, Eastern Europe, Asiaor
 - North America, Eastern Europe, Western Europe + Asia if the percentage of randomized subjects is less than 10% in either of the Asia or Western Europe regions

- Prior TNF α inhibitor exposure (inadequate response to 1 prior TNF α inhibitor, inadequate response to 2 prior TNF α inhibitors, intolerance to TNF α inhibitors)

When adjusting on these 2 variables, a statistical model might not converge (ie, in case the likelihood maximization algorithm failed to converge). In that case, the statistical model will be run after dropping stratification variables in their order of appearance, successively region (one first and the other after) and prior TNF α inhibitor exposure.

In the event that a subject is stratified in the incorrect stratum (ie, the stratum recorded in the Interactive voice or web Response System (IXRS) differs from the actual stratum the subject belongs to), the actual stratum will be used for the analysis.

The secondary analyses will be adjusted on the same categorical factors as the primary analysis. For continuous variables, Baseline value (of the variable of interest) will also be included as covariate where appropriate.

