4.2.2.2 Composite binary endpoints

For composite binary endpoints, the MI method will be applied as follows:

- **Step 1:** The MCMC/monotone regression approach described above in Step 1 for non-composite binary endpoints will be performed separately for each individual component variable.

- **Step 2:** The same rounding rules described in Step 2 above for non-composite binary endpoints will be performed for each component.
- **Step 3:** Based on the multiple imputed data sets obtained for each component, the binary response will be derived as follows:
 - The dataset obtained for each component will be merged by imputation number and subject number
 - On the dataset obtained, the binary endpoint will be derived for each subject/visit based on the component values.
 - If subjects have an IE, then the endpoint at all subsequent visits (from the day after the intercurrent event date, whether the data were observed or not) will be set to “non-response”.
- **Steps 4 and 5:** Same as Steps 4 and 5 above for non-composite binary endpoints ([Section 4.2.2.2.1](#)).

For the primary endpoint, the ‘burn-in’ option in SAS® PROC MI may be set higher than the default value. The goodness-of-fit tests to assess convergence of the MCMC will be provided in a SAS® output.

4.2.2.2.3 Calculation of adjusted responder rates, odds ratio and CIs for binary endpoints.

Estimates of the adjusted responder rates for each treatment group and the associated standard errors are obtained from the logistic regression in Step 5 on the logit scale and as such are assumed to follow a normal distribution. These estimates will be combined using Rubin’s rules and the combined estimates and associated SEs will be used to construct 95% CIs on the logit scale. The combined estimates and 95% CIs on the logit scale will be back transformed using the inverse logit link function to obtain the adjusted responder rates (%) and associated 95% CIs.

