Some key points to consider relative to the calculation of the odds ratios and corresponding confidence intervals. As the estimates of the odds ratios from the logistic regression model in step 5 follow a lognormal distribution, a log transformation is needed to normalize these 100 odd-ratio estimates since the procedures for combining results from multiple imputed datasets are based on the assumption that the statistics estimated from each imputed dataset are normally distributed. Therefore, the log of the odds ratio estimates from the logistic regression model are used when combining into a single inference (step 3). Additionally, the standard errors (SE) for the odds ratios are transformed as follows:

$$SE = \frac{\log(UCL) - \log(LCL)}{2Z_{\alpha/2}}$$

where UCL and LCL are the upper and lower confidence limit, respectively, for the CI of the odds ratio from the logistic regression model, and $Z_{\alpha/2}$ is the relevant critical value from the standard normal distribution (1.96 for a 95% CI). The estimates of the log odds ratio for BKZ relative to placebo and the corresponding upper and lower confidence limits will be provided. The odds ratio will be then estimated by exponentiating the estimate of the log odds ratio. The odds ratio and the confidence limits of the odds ratio will be estimated as follows:

$$OR = \exp(\text{Log odds ratio estimate})$$

$$LCL = OR * \exp(-SE * Z_{\alpha/2})$$

$$UCL = OR * \exp(SE * Z_{\alpha/2})$$

where OR is the back-transformed estimate of the odds ratio just described, SE is the standard error of the log odds ratio and $Z_{\alpha/2}$ is the relevant critical value from the standard normal distribution (1.96 for a 95% CI). These calculations will be done such that odds ratios and corresponding CIs are calculated for the odds ratio of BKZ versus placebo.

In addition to calculating the odds ratio, associated CIs, and p-values for the comparisons of BKZ vs. placebo, the estimated proportion of responders (ie, estimated responder rate) and the difference in the proportion of responders between BKZ and placebo will be estimated, along with 2-sided 95% CIs. The creation of the estimates of this difference will be completed using the process detailed below:

1. Use the logistic regression model to calculate:

Least squares mean (LSM) estimates of the log odds of BKZ (G_B) and placebo (G_P), as well as their corresponding standard errors (S_B and S_P , respectively).

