Standard error of the LSM estimate of the log odds ratio (S_R)

2. Compute estimates for predicted proportions using the following transformations:

$$P_B = \exp(G_B)/(1 + \exp(G_B))$$

$$P_P = \exp(G_P)/(1 + \exp(G_P))$$

The difference in proportions is then given by:

$$D = P_B - P_P$$

3. Estimate the standard error of D by:

$$SD = \text{sqrt}[P_B^2(1-P_B)^2S_B^2 + P_P^2(1-P_P)^2S_P^2 + P_B(1-P_B)P_P(1-P_P)S_R^2 - P_B(1-P_B)P_P(1-P_P)(S_B^2 + S_P^2)]$$

The MI/MCMC monotone regression method, as previously outlined, will be used to account for missing values. The calculation steps described above will be based on the results provided from the logistic regression model of the multiple imputed datasets. An estimate for the difference in proportions, D, and corresponding standard error, SD, will be computed for each of these datasets. The results from these analyses will be combined into a single estimate of the difference in predicted proportion of response and a 2-sided 95% CI interval using SAS PROC MIANALYZE.

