8.1.2 Primary analysis of the primary efficacy variable

The primary efficacy variable will be analyzed for all subjects in the RS.

The primary endpoint is the ACR50 response at Week 16. The primary efficacy analysis will evaluate the composite estimand in the RS. The composite estimand combines the clinically meaningful improvement from Baseline in ACR components as assessed using the ACR50 response at Week 16 and not discontinuing study treatment prior to Week 16.

The following 4 attributes describe the estimand that will be used to define the treatment effect of interest for the primary efficacy analysis:

- Population = Subjects enrolled according to the protocol-specified inclusion/exclusion criteria and randomized to IMP
- Subject-level outcome = ACR50 at Week 16
- Intercurrent event handling = An intercurrent event is defined as discontinuation of study treatment prior to Week 16. A composite strategy will be implemented in which a positive clinical outcome is defined as achieving ACR50 at Week 16 and not discontinuing study treatment through Week 16.
- Population-level summary measure = Conditional odds ratio comparing BKZ to placebo and difference of response rate between BKZ and placebo.

Missing data at Week 16 that are not preceded by an IE and any data after an IE will be imputed as non-responders. This results in a more traditional NRI approach and will be labeled as such throughout the SAP.

The statistical hypothesis for the ACR50 response at Week 16 is that the conditional OR for ACR50 response in the BKZ treatment compared to placebo treatment is equal to 1.

A logistic regression model will be used to assess the treatment effect on ACR50 response at Week 16. The model will include fixed effects for treatment, and prior TNF α inhibitor exposure and region as stratification factors. The suitability of including these variables in the model will be assessed using Pearson and Deviance and the Hosmer-Lemeshow Goodness-of-Fit Tests (Hosmer and Lemeshow, 2000).

P-values below 0.05 would lead to a reconsideration of the model to be used and if the logistic regression model is unable to converge the stratification variables will be dropped ([Section 4.1](#)). In that case, all supportive analyses as well as imputation models conducted for the primary endpoint will disregard these exploratory factors from their models.

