The country-specific analyses performed on subjects randomized in Japan will not consider the region factor as a covariate for the modelling. Considering that the number of subjects randomized in Japan is low (less of 10% of the RS), statistical models might not converge. If a model (logistic Model or mixed model) is not converging, all related adjusted statistics and p-value will not be presented; “NE” for “Not Evaluable” will be displayed instead.

The SAS® PROC LOGISTIC will be used to run the logistic regression.

The summary table results will present the adjusted responder rates and the associated 95% CI for BKZ and placebo, the adjusted odds ratio and 95% CI for the comparison of BKZ versus placebo, and the p-value that the OR=1 and the difference of response rate between BKZ and placebo and associated 95% CI. The treatment comparison will be made using the 2-sided Wald test at a significance level of $\alpha=0.05$ (ie, H_1 in [Table 7-4](#)).

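### The adjusted response rates and their difference are back-transformed LS-means with no stated weighting or target population, so they need not estimate the randomised-population difference that the primary estimand names

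*SAP*

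**What the plan says.** Section 8.1.2 sets the estimand population as "Population = Subjects enrolled according to the protocol-specified inclusion/exclusion criteria and randomized to IMP" and the summary measure as "Conditional odds ratio comparing BKZ to placebo and difference of response rate between BKZ and placebo". The rate difference with its 95% CI is a required output of the primary analysis. Section 8.2.2 asks for the secondary binary endpoints to be presented in the same way.

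The model is a main-effects logistic regression: "The model will include fixed effects for treatment, and prior TNF α inhibitor exposure and region as stratification factors". On software, "The SAS® PROC LOGISTIC will be used to run the logistic regression".

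Section 4.2.2.2.3 gives the computation. Adjusted rates are logit-scale estimates that are "back transformed using the inverse logit link function to obtain the adjusted responder rates (%) and associated 95% CIs". For the difference, step 1 takes "Least squares mean (LSM) estimates of the log odds of BKZ" and the same for placebo. Step 2 is "Compute estimates for predicted proportions using the following transformations": the inverse logit in each arm, then a subtraction. Step 3 gives a standard error.

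That section belongs to the multiple-imputation text. Section 8.1.2 uses non-responder imputation and asks for the same outputs, but neither cites 4.2.2.2.3 nor gives another method. No section says how LS-means are weighted over region and prior TNFα inhibitor exposure.

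Section 4.1 expects uneven regions: Western Europe and Asia are pooled "if the percentage of randomized subjects is less than 10% in either of the Asia or Western Europe regions".

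**The concern.** An LS-mean is a weighted average of model predictions over the covariate levels, so it has no defined target until the weights are fixed. In the usual balanced form each region counts 1/4 (1/3 after pooling) and each prior-TNFα category 1/3, whatever their sizes. If the strata differ in both size and response, the inverse logit of that average is not the response rate of the randomised subjects. The difference of two such values is not their rate difference either.

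At stake is a named summary measure of the primary estimand, with its confidence interval, and the matching displays for the other binary endpoints in the hierarchy. This is the absolute benefit that readers will take from the trial.

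**Working it through.** **The plan's own figure.** For 26% vs 10%, 260:130, two-sided 0.05, with the continuity-corrected formula, I obtain 96.6% power against the stated 96%. The odds ratio is (0.26/0.74)/(0.10/0.90) = 3.16, as stated. Neither figure is in dispute; the rates serve as the planning truth below.

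**Inputs from the SAP.** Marginal rates are 26% and 10%, so the true difference is 16.0 points. There are four regions, three prior-TNFα categories and no treatment interaction.

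**Inputs assumed, because the SAP gives none.** Region shares are 25/15/50/10% and prior-TNFα shares 75/12/13%. The stratum effects are d log-odds for the largest region against the others, and −d for the two smaller TNFα categories against the largest, with d = 0.3 or 0.5. Signs are then reversed or opposed.

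**Method.** Write the logit as a + b·(BKZ) + region effect + TNFα effect. Solve for a and b so that the share-weighted average probabilities are exactly 10% and 26%. Then compute P = expit(weighted mean logit) in each arm and subtract, as in Section 4.2.2.2.3.

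**One case in full (d = 0.5, largest strata respond best).** The solution is a = −2.3647, b = 1.1675.
- Balanced weights: mean shift = 0.5/4 − (0.5 + 0.5)/3 = −0.208. The LS-means are about −2.573 (placebo) and −1.406 (BKZ). The rates are 7.1% and 19.7%, a difference of 12.6 points.
- Observed-margin weights: mean shift = 0.50×0.5 − (0.12 + 0.13)×0.5 = 0.125. The rates are 9.6% and 25.5%, a difference of 15.9 points.

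**All cases (true difference 16.0 points):**

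| Assumed stratum effects | Balanced weights, BKZ / placebo / difference | Observed-margin difference |
|---|---|---|
| None | 26.0 / 10.0 / 16.0 | 16.0 |
| 0.3, largest strata respond best | 22.2 / 8.2 / 14.0 | 16.0 |
| 0.5, largest strata respond best | 19.7 / 7.1 / 12.6 | 15.9 |
| 0.3, reversed | 29.8 / 11.8 / 18.0 | 16.0 |
| 0.5, reversed | 32.3 / 12.9 / 19.4 | 15.9 |
| 0.3, region and TNFα effects opposed | difference 15.4 or 16.5 | 16.0 |
| 0.5, region and TNFα effects opposed | difference 15.0 or 16.8 | 15.9 |

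Standardisation over the observed covariates returns 16.0 in every row by construction.

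**Pooling.** If Western Europe and Asia were pooled, the region weight would change from 1/4 to 1/3. With nothing else altered, the d = 0.5 results move from 12.6 to 13.0, and from 19.4 to 19.0 when reversed.

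**Standard error.** Let A = P_B(1−P_B) and C = P_P(1−P_P). The delta method gives Var(D) = A²S_B² + C²S_P² − 2AC·Cov. Because S_R² = S_B² + S_P² − 2Cov, the last term equals AC(S_R² − S_B² − S_P²). That is the SAP's formula, so the variance is right for the quantity computed. The question is only which quantity that is.

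**The case against.** - **The SAP nowhere writes equal weights.** A reader might infer that it prescribes a balanced average. It names only LS-means and the SAS procedure. Balanced weighting is the usual meaning, but with observed margins the gap all but disappears. This stands: the documented defect is an unstated weighting and target, and the gap above is its consequence under the ordinary reading.
- **The formula sits in the multiple-imputation section**, and Section 8.1.2 does not cite it. Its use for the primary analysis is therefore an inference. It is a reasonable one, since the same outputs are requested and no other method exists. If it does not apply, the primary rate difference has no specified method at all.
- **The quantity is not exactly the risk difference of an equal-strata population**, because a mean logit is back-transformed. In the d = 0.5 case that risk difference is 12.8 against 12.6. This stands, and it is small.
- **A reader might infer that the benefit will be understated.** The documents do not support a direction: no shares or stratum effects are given, and the gap can go either way or be under 1 point.
- **Unadjusted rates are also reported.** Section 8.3.2.2 gives observed proportions under non-responder imputation by visit, and Step 4 of Section 4.2.2.2.1 does so for the imputed data. A reader could notice a divergence. That limits the harm, but does not supply an adjusted difference with a CI for the randomised population.
- **A reader might infer that the primary test is compromised.** It is not. The hypothesis is that the conditional odds ratio equals 1, tested by a Wald test that does not use these rates.

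**Conclusion.** The point holds in a limited form. The estimand names a rate difference in randomised subjects, while the only stated computation leaves the LS-mean weighting open. Under the usual balanced weights and unequal strata, it does not estimate that difference. For a true 16.0 points, the balanced result lies between about 12.6 and 19.4. It stays within about 1 point when the region and TNFα effects oppose each other (four regions), and there is no gap when the covariates do not predict response.

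These sizes rest on assumed shares and assumed effects of 0.3 to 0.5 log-odds; the mechanism does not. The consequence is confined to the adjusted rates, their difference and the corresponding intervals. It is worth correcting because the difference is part of the primary estimand and the correction leaves the inference unchanged.

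**What to change.** State in Sections 8.1.2 and 4.2.2.2.3 that the adjusted rates and their difference are standardised over the observed covariates of the Randomized Set. Predict each subject's response probability under BKZ and under placebo from the fitted model, average over subjects, subtract, and use a delta-method standard error. Combine by Rubin's rules where multiple imputation is used. For PASI90, average over the randomised subjects in that endpoint's BSA subgroup. At minimum, specify observed-margin weights for the LS-means and name the target population. Have Section 8.1.2 cite the method explicitly. Keep the odds ratio and Wald test as planned.

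The cost is a few lines of SAP text and a short macro. The adjusted rates will no longer match default LS-mean output; no test or sample-size figure changes.

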4.2.2.2.4 Continuous efficacy endpoints

For secondary and other continuous efficacy endpoints, the same methods as the ones described above for the non-composite binary endpoints will apply based on the values at the timepoint(s) of interest, with the following differences:

- Step 1: The same imputation procedure as the described in step 1 for the non-composite binary endpoints will be used.

- Step 2: The same rounding rules described in step 2 above for non-composite binary endpoints will be performed.
- Step 3: On the dataset obtained with the imputation number from 1 to 100; change from Baseline will be derived. Simple means and standard errors will be calculated using Rubin's rules (via SAS® PROC MIANALYZE) for each timepoint(s) of interest. For calculation of other descriptive statistics such as the median, min and max, Rubin's rules do not apply. MI estimates will be computed by simply averaging the estimates from the multiple repetitions of the imputation algorithm. For CRP data (that will be presented using the geometric mean and corresponding 95% CI, arithmetic mean, median, Q1, Q3, minimum and maximum). The change from Baseline will be expressed as the ratio to Baseline (value at the visit divided by value at Baseline) in the by-visit summaries. The following approach will be applied:
 - Following the MI procedure, the ratio to Baseline will be calculated for any of the imputed values
 - The natural logarithm of the absolute values and of the ratios to Baseline will be calculated
 - The logged values will be summarized by treatment, visit and imputation
 - The datasets will be combined using PROC MIANALYZE in order to get the mean from the absolute values and ratios to Baseline across imputations
 - The estimates of the mean will be back transformed to obtain the geometric mean on the original scale
 - For the median, Q1, Q3, minimum and maximum the procedure outlined above for the other endpoints will be followed
- Step 4: (for primary and secondary efficacy variables): For each value of the imputation number from 1 to 100, the change from Baseline will be analyzed using an ANCOVA model with treatment group, region, and prior TNF α inhibitor exposure as fixed effects and the Baseline value as covariate. The results obtained from the 100 ANCOVA analyses (ie, the LSM for the treatment difference and the 95% CI for the contrasts) will be combined using Rubin's rules (via SAS® PROC MIANALYZE).

For composite continuous endpoints, the MI will be applied on each component the same way as for composite binary endpoint. The datasets obtained for each component will be merged by imputation number and subject number. On the dataset obtained, the endpoint will be derived for each subject/visit based on the component values. The endpoint obtained will be analyzed as above.

4.2.2.2.5 Ordinal efficacy endpoints

For ordinal efficacy endpoints, the MI method will be applied as for the continuous efficacy endpoints with the following exceptions:

- After the imputation of the intermittent and monotone missing data, the rounding rules will be performed to align the data with the possible responses for the respective endpoint (eg, If the variable can take the value 1, 2 or 3, the imputed values will be rounded to the closest possible value).

- If the ordinal efficacy endpoint is used to derive a binary endpoint, the same analysis strategy as described above for the binary endpoints will be used.
- If the ordinal efficacy endpoint is not used to derive a binary endpoint, the unadjusted proportions of subject by categories will be presented.
- If subjects have an IE, then the ordinal endpoint at all subsequent visits (from the day after the IE date, whether the data were observed or not) will be set to the value used for the worst category.

4.2.2.3 MI – MCMC/Reference-Based imputation

For the primary analysis of the secondary continuous efficacy variable included in the testing hierarchy and the individual components of the ACR response, the Reference-Based multiple imputation method will be used. In this imputation method, the missing data will be imputed based on data from the placebo group only (Mallinckrodt, 2013).

Reference-Based MI assumes that the statistical behavior of the BKZ and placebo-treated subjects after discontinuing study medication becomes that of the placebo-treated subjects. All time points after study treatment discontinuation for BKZ and placebo groups will be considered missing. MIs are used to replace missing outcomes for BKZ- and placebo-treated subjects who discontinued using multiple draws from the posterior predictive distribution estimated from the placebo arm.

Note: SAS 9.4 may be used for this analysis where equivalent steps to those outlined below will be used to perform the imputation.

In the case of continuous endpoints, the procedure will be implemented as follows on the raw values:

1. Data will be processed sequentially, one timepoint (visit) at a time, by repeatedly calling SAS[®] PROC MI to impute missing outcome data at visits $t=1, \dots, \text{Week 16}$ (Week 16 being the time point of interest) using data from the placebo-treated subjects arm only.
 - a. *Initialization.* Set $t=1$ (Baseline visit). Create a dataset combining all records from all subjects with columns for covariates (prior TNF α exposure and region) and outcome at Baseline. Impute missing values at Baseline using prior TNF α exposure at Baseline and region.
 - b. *Iteration.* Set $t=t+1$. Create a dataset combining records from BKZ- (subjects with missing data at visit t) and all placebo-treated subjects with columns for covariates (prior TNF α exposure and region) and outcomes at visits 1 to t . In this dataset, outcomes for BKZ-randomized subjects are missing at visit t and observed or previously imputed at visits 1 to $t-1$. Outcomes for placebo-treated subjects are observed or missing at visit t and observed or previously imputed at visits 1 to $t-1$. The outcomes should be sorted in chronological order in the model.
 - c. *Imputation.* Impute missing values for visit t using previous outcomes for visits 1 to $t-1$, prior use of TNF α inhibitor, and region. Note that only placebo data will be used to estimate the imputation model since no outcome is available for BKZ- treated subjects at visit t . As a consequence, the input dataset should include all subjects from placebo but only subjects from the BKZ arm that have values at timepoint t missing.

- d. Repeat steps 1b-1c for all timepoints, 100 times with different seed values (seeds ranging from 201 to 300) to create 100 imputed complete datasets. Subjects whose missing values were imputed in the last PROC MI call will be included in the input dataset for the next PROC MI call. Standard rounding rules will be applied to the imputed values. If the MI procedure yields a value outside of the pre-defined range for the given variable, the value will be updated to be within the predefined range of values for the endpoint of interest. For example, the imputed value for TJC will be updated to 0 or 68 in the case of an imputed value less than 0 or greater than 68, respectively.
2. The analysis will be done on the change from Baseline, and the model will be an ANCOVA model with treatment group, region, and prior TNF α inhibitor exposure classification as fixed effects and the Baseline value as covariate.

For generation of summary statistics, the 100 imputed datasets will be combined, and simple means and standard errors will be calculated using Rubin's rules (via SAS[®] PROC MIANALYZE). For calculation of other descriptive statistics (median, Q1, Q3, minimum and maximum), Rubin's rules do not apply. Multiple imputation estimates will be computed by calculating arithmetic means of the estimates from the multiple repetitions of the imputation algorithm. Thus, for median, Q1, Q3, minimum and maximum the following approach will apply:

- The data will be summarized by treatment, visit and imputation and the summary statistics will be computed.
 - Results will be summarized by taking the mean value of each summary statistic at each visit across all imputations.
 - The number of decimal places will remain the same as the original for display purposes (ie, if the mean was presented to 1 decimal place, the mean of the means will also be presented to 1 decimal place).
3. The results obtained from the 100 ANCOVA analyses in Step 4 (i.e. the Least Square Means for the treatment difference and the 95% CI for the contrasts) will be combined with Rubin's rules.

